5.3.1.2.2 Pharmacogenetic Samples

Subjects will have the option to provide samples for exploratory research. Subjects may still participate in the main study even if they decide not to participate in this optional exploratory research.

AbbVie (or people or companies working with AbbVie) will store the exploratory research samples in a secure storage space with adequate measures to protect confidentiality. The samples will be retained while research on ABBV-8E12 (or drugs of this class) or PSP and related conditions continues, but for no longer than 20 years after study completion. The procedure for obtaining and documenting informed consent for exploratory research samples is discussed in Section 9.3. Instructions for the preparation and shipment of the exploratory research samples will be provided in a laboratory manual.

Optional whole blood samples (6.5 mL) for DNA and RNA isolation will be collected at the times indicated in the Study Activities Table ([Appendix C](#)).

All pharmacogenetic samples should be collected, processed, labeled and shipped as outlined in the study-specific laboratory manual, which will be provided separately.

5.3.1.3 Confinement

No confinement will be required for this study.

5.3.1.4 Meals and Dietary Requirements

There are no dietary requirements or restrictions for this study.

5.3.2 Drug and Anti-Drug Antibody Concentration Measurements

5.3.2.1 Collection of Samples for Analysis

Specific instructions for collection of blood samples and subsequent preparation and storage of the serum samples for the pharmacokinetic assays of ABBV-8E12 will be provided by the central laboratory, the Sponsor, or its designee.

5.3.2.1.1 Blood Samples for ABBV-8E12 Assay

Blood samples (approximately 3 mL) for ABBV-8E12 analysis will be collected by venipuncture at the times indicated in the Study Activities Table ([Appendix C](#)) as follows:

- **Day 1 (Dose 1)**
 - Prior to the start of the infusion (0 hour), immediately after the end of the infusion (within 15 minutes) and 1 and 2 hours after the end of the infusion
- **Weeks 12, 24, 52, 76, 104, 128, 156, 180, 208, 232, and 260**
 - Prior to the start of the infusion (0 hour), when applicable (no dose at Week 260)
- **Post-Treatment Follow-up Visit (20 weeks after last dose)**
 - Sample may be collected any time during the visit

PK samples collected prior to infusion (0 hour) should be collected no more than 30 minutes prior to the start of infusion. The allowable PK window for 1-hour postdose

samples is ± 6 minutes, and the allowable PK window for 2-hour postdose samples is ± 12 minutes. The allowable window for samples scheduled for the post-treatment Follow-Up Visit is ± 4 days.

5.3.2.1.2 Blood Samples for ABBV-8E12 Anti-Drug Antibodies (ADA) Assays

Blood samples (approximately 3 mL) for ABBV-8E12 ADA analysis will be collected by venipuncture at the times indicated in the Study Activities Table ([Appendix C](#)) as follows:

- **Day 1 (Dose 1)**
 - Prior to the start of the infusion (0 hour)
- **Weeks 12, 24, 52, 76, 104, 128, 156, 180, 208, 232, and 260**
 - Prior to the start of the infusion (0 hour), when applicable (no dose at Week 260)
- **Post-Treatment Follow-up Visit (20 weeks after last dose)**
 - Sample may be collected any time during the visit

The ADA samples collected prior to infusion (0 hour) should be collected no more than 30 minutes prior to the start of infusion. Blood samples may be collected within ± 4 days for the post-treatment Follow-up Visit.

5.3.2.1.3 CSF Samples for ABBV-8E12 Assay

CSF samples (assessment referred to as lumbar puncture) will be collected at the times indicated in the Study Activities Table ([Appendix C](#)).

The collection time and procedures of CSF samples are located in the lumbar puncture section of Study Procedures Section (Section [5.3.1.1.12](#)).

5.3.2.2 Measurement Methods

Serum concentrations and relative titers in serum of ABBV-8E12 ADA will be determined using validated methods at the Bioanalysis Department at AbbVie. CSF

concentrations of ABBV-8E12 will be analyzed using qualified or validated methods. Any additional analytes may be analyzed using non-validated methods either at AbbVie or by outside vendors or collaborators. Serum samples collected for ABBV-8E12 and ABBV-8E12 ADA analysis may be used for future assay development or validation activities. ABBV-8E12 ADA samples may be used for the analysis of neutralizing anti-drug antibodies.

5.3.3 Efficacy Variables

5.3.3.1 Primary Variable

The primary efficacy variable will be the PSPRS total score to assess the effect of ABBV-8E12 in slowing disease progression.

5.3.3.2 Secondary Variables

Key secondary efficacy measures are as follows:

- UPDRS Part II
- CGI-C
- SEADL

Additional secondary efficacy measures are as follows:

- CGI-S
- PGI-C
- PSP-SS (composite of items from PSPRS)
- Time to loss of ability to walk independently as measured by PSPRS item 26

Analysis of the secondary efficacy variables obtained from these measures is detailed in Section 8.0.

5.3.3.3 Exploratory Variables

Exploratory efficacy measures are as follows:

- Time to death
- EQ-5D
- Letter Fluency Test (words per minute)
- RBANS
- CTT (Parts 1 and 2)
- NNIPPS-PPS (not applicable in Japan)
- Frequency of hospitalizations related to PSP

Analysis of the exploratory efficacy variables obtained from these measures is detailed in Section 8.0.

5.3.4 Safety Variables

Adverse events and SAEs will be monitored throughout the dosing period and for approximately 20 weeks after the last dose. Safety evaluations will consist of the following: monitoring of adverse events (including infusion and allergic reactions), vital signs, physical examination, complete neurologic exam, cognitive assessments, C-SSRS, laboratory abnormalities, ECG, brain MRI including FLAIR, and immunogenicity as determined by ADA responses in blood.

5.3.5 Pharmacokinetic Variables

The concentration of ABBV-8E12 will be determined in serum and CSF samples collected in the study. Data from this study may be combined with data from other ABBV-8E12 studies for pharmacokinetic analyses.

A mixed-effect modeling approach will be used to estimate the population central value and obtain empirical Bayesian estimates of the individual values for ABBV-8E12 clearance (CL) and volume of distribution (V).

The concentration of ABBV-8E12 in CSF will be summarized at each collection time point.

Additional parameters may be calculated if useful in the interpretation of the data.

5.3.6 Biomarker and Pharmacogenetic Research Variables

5.3.6.1 Biomarker Research Variables

Blood and CSF samples will be collected to conduct research to investigate disease related and drug-related biomarkers. The biomarkers to be analyzed may include, but are not limited to, the following:

- CSF and Plasma Biomarkers:
 - Tau in CSF and plasma
 - Additional exploratory CSF and plasma-based pharmacodynamic analyses may be conducted based on sample availability
- Imaging Biomarkers:
 - Regional and/or whole brain volume derived from MRI
 - Fractional anisotropy and diffusivity measures in brain regions of interest derived from DTI
- Digital Biomarkers:
 - BioStamp sensor motor outcomes including posture, gait, and step count

Exploratory evaluations from blood and CSF samples may include analyzing biomarkers related to the pathway(s) targeted by the study drug or believed to be related to the disease or to drug response.

The information learned from analyzing these data may be used to investigate factors impacting response to treatment, scientific questions related to PSP, support development of ABBV-8E12, or in the development of new therapies. Furthermore, given the exploratory nature of these data the results may not be included in the study summary.

Digital substudy endpoints will be handled in a separate scientific report.

5.3.6.2 Pharmacogenetic Research Variables

Optional samples may be collected to conduct exploratory investigations into known and novel biomarkers. The types of biomarkers to be analyzed may include, but are not limited to, nucleic acids, proteins, lipids or metabolites. The samples may be analyzed as part of a multi-study assessment of factors influencing the subjects' response to the study drug (or drugs of the same or similar class) or the development and progression of the subjects' disease or related conditions. The samples may also be used to develop new diagnostic tests, therapies, research methods or technologies. The results from these analyses are exploratory in nature and may not be included with the study report.

5.3.7 Immunogenicity

ADA levels will be determined for the assessment of immunogenicity.

5.4 Removal of Subjects from Therapy or Assessment

5.4.1 Discontinuation of Individual Subjects

Each subject has the right to withdraw from the study at any time. In addition, the investigator may discontinue a subject from the study at any time if the investigator considers it necessary for any reason, including the occurrence of an adverse event or noncompliance with the protocol.

The subject will be discontinued from the study if any of the following occur:

- Subject starts receiving an approved therapy for PSP.
- Subject develops unacceptable toxicity.
- Female subject becomes pregnant.
- Investigator decides it is in the subject's best interest to discontinue.
- Subject is noncompliant with the protocol based on the investigator or medical monitor assessment.
- Subject withdraws consent.

- Subject is lost to follow-up despite reasonable efforts by the investigator to locate the subject.

Severe allergic reactions or other adverse events that require the immediate interruption of ABBV-8E12 treatment will be taken into consideration by the AbbVie TA MD for permanent discontinuation from further treatment and initiation of appropriate medical therapy and follow-up.

Any treatment-emergent, clinically significant, symptomatic neurological abnormalities and treatment-emergent MRI findings will be reported to the AbbVie TA MD and subjects will be considered for discontinuation from treatment if clinically indicated.

Subjects at risk of suicide as indicated by answering yes to question 4 or 5 on the C-SSRS and/or determined by the investigator to be at risk of suicide, should be promptly referred for appropriate follow-up care. Subjects determined to be at ongoing risk of suicide should be discontinued from study participation.

If for any reason the subject becomes unable to continue treatment with ABBV-8E12, undergo protocol required procedures, or otherwise continue to participate in the study, discontinuation should be discussed with the AbbVie TA MD.

In the event that a subject withdraws or is discontinued from the study, the primary reason for discontinuation and any other reason(s) for the discontinuation from the study will be recorded and a physical examination, neurological examination, body weight, vital signs measurement, ECG, laboratory analyses, MRI, lumbar puncture, administration and completion of scales/questionnaires, C-SSRS, a serum pregnancy test (WOCBP only), and an assessment of adverse events and concomitant medications will be performed as soon as possible after discontinuation from the study (Refer to Study Activities Table, [Appendix C](#)). Additional blood samples for drug measurement may be collected at the time of discontinuation from subjects who are discontinued due to adverse events; the clock time, time in relation to dose, and date the sample was collected will be recorded.

If a subject is discontinued from the study with an ongoing adverse event or an unresolved laboratory result that is significantly outside of the reference range, the investigator will attempt to provide follow-up until a satisfactory clinical resolution of the laboratory result or adverse event is achieved.

In the event that a positive result is obtained on a pregnancy test for a subject or a subject reports becoming pregnant during the study, the administration of study drug to that subject must be discontinued immediately. The investigator must report a pregnancy within 1 working day of the site being aware to one of the AbbVie representatives listed in Section 6.1.5 or Section 7.0.

Subjects who prematurely discontinue from the study can be contacted by telephone for periodic updates at the times shown in [Appendix C](#) providing that consent for this contact was obtained prior to contact being made.

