3.2 Benefits and Risks

Patients with PSP suffer serious debilitating symptoms that affect gait and balance, vision, swallowing and speaking, and cognition. The disease is characterized by tau aggregation and is ultimately fatal. No approved treatment exists.

ABBV-8E12, a humanized monoclonal antibody that is being developed for the treatment of PSP, may block tau seeds from propagating between cells, and therefore, may slow disease progression, thus providing a viable treatment option for patients with PSP. The safety profile of ABBV-8E12 to date has been favorable, and no clinically relevant patterns of adverse events or abnormal laboratory findings have been observed. Further, no ADAs were detected in postdose samples in an SAD study in subjects with PSP.

Risks include infusion reactions and possibly life-threatening allergic reactions; however, no systemic hypersensitivity or injection site reactions have been reported to date. Subjects will be monitored closely during clinical trials for the occurrence of these events, study drug will be withdrawn immediately in the case of allergic reaction, and appropriate medical therapy will be provided for any adverse event.

Evidence of efficacy demonstrated in preclinical studies and safety data from clinical studies obtained to date provide a strong rationale for continuing the assessment of safety and efficacy of ABBV-8E12. The benefit-risk profile of ABBV-8E12 will be further defined in Study M15-562, which is ongoing, and in Study M15-563, which is described herein.

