6.1.7.3 Non-Specific Off-Target Toxicities

Potential toxicities resulting from the non-human origin of ABBV-8E12 include allergic reactions or infusion reactions, including anaphylaxis or anaphylactoid reactions, flu-like symptoms, including fever, fatigue or loss of appetite, or rash. ABBV-8E12 is lacking the Fragment Crystallizable (Fc) effector function activity and therefore Fc-mediated antibody-dependent cellular cytotoxicity and complement-dependent cytotoxicity is not expected. In addition, ABBV-8E12 exhibited a favorable in vitro immune-safety profile. No infusion reactions have occurred in the single dose PSP clinical study or in the Expanded Access protocol (Studies C₂N-8E12-EA-001 and C₂N-8E12-DE-003).

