6.1.7.4 Allergic Reactions Management

Subjects will be closely monitored for treatment-related adverse events, including allergic reactions, during the infusion. Subjects should be monitored on site for at least 30 minutes after the end of study drug infusions. Longer observation periods and more frequent vital sign checks may be required in subjects who experience infusion reactions.

Severe or life-threatening allergic reactions require the immediate interruption of ABBV-8E12 treatment and permanent discontinuation from further treatment. Appropriate medical therapy including epinephrine, corticosteroids, IV antihistamines,

bronchodilators, and oxygen should be available for use in the treatment of such reactions. Subjects should be carefully observed until the complete resolution of all signs and symptoms.

Moderate infusion reactions resolving with supportive care should be discussed with the TA MD, and a reduction of the infusion rate for future administrations can be considered.

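### Protocol Section 5.4.1 leaves permanent discontinuation after a severe allergic reaction to the sponsor's medical director, where Section 6.1.7.4 makes it mandatory

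*Protocol*

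**What the plan says.** Protocol Section 5.4.1 lists criteria that always lead to discontinuation, then treats allergic reactions in a sentence of their own. Its subject is "Severe allergic reactions or other adverse events that require the immediate interruption of ABBV-8E12 treatment", and its action is that these "will be taken into consideration by the AbbVie TA MD for permanent discontinuation from further treatment".

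Protocol Section 6.1.7.4, on the management of allergic reactions, begins its rule with "Severe or life-threatening allergic reactions require the immediate interruption of" ABBV-8E12 and completes it with "treatment and permanent discontinuation from further treatment". A lower tier follows: "Moderate infusion reactions resolving with supportive care should be discussed with the TA MD", with a slower rate possible at later infusions.

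A third statement is in Protocol Section 3.2: "study drug will be withdrawn immediately in the case of allergic reaction". It sets no severity threshold and does not say whether withdrawal is permanent.

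**The concern.** One event has two rules. Under Section 5.4.1 the TA MD weighs whether the subject stops for good. Under Section 6.1.7.4 the subject stops for good and nothing is left to weigh. Stopping the infusion under way is not in dispute. The open question is whether dosing could resume.

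This is a matter of patient safety. Section 3.2 describes allergic reactions as possibly life-threatening, and Section 6.1.7.3 names anaphylaxis among the potential toxicities. Subjects coming from placebo receive their first ABBV-8E12 in this study, and dosing is planned for up to 5 years, so an early reaction could leave many scheduled infusions to decide about.

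**Working it through.** The plan gives no figure to reproduce. The check is a comparison of the current text, followed by one count of scheduled doses.

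**1. Do the two sentences cover the same events?** Section 5.4.1 refers to reactions that require immediate interruption, which might seem to select a subset. It does not, because Section 6.1.7.4 says that every severe or life-threatening allergic reaction requires interruption. Nor are life-threatening reactions a class outside Section 5.4.1: the severity scale in Section 6.1.2 puts potentially life-threatening events in the severe grade.

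**2. Do the actions agree?**

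| Event | Section 5.4.1 | Section 6.1.7.4 |
|---|---|---|
| Severe or life-threatening allergic reaction | TA MD considers a permanent stop | Permanent stop required |
| Moderate infusion reaction that resolves with supportive care | Not addressed separately | Discussed with TA MD; slower rate possible |

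Section 6.1.7.4 is tiered, and TA MD discussion belongs to the lower tier. Section 5.4.1 sends the upper tier to TA MD judgment.

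**3. Does other text settle it?**
- Section 5.6.1 says that toxicity management is found in Section 6.1.7. The introduction to Section 6.1.7 says that its guidelines should be used for toxicity related to study drug. Both point towards the mandatory rule. Neither says that it overrides Section 5.4.1.
- Unacceptable toxicity is a compulsory criterion in Section 5.4.1, but it is not defined, and the same section handles severe allergic reactions separately.
- Section 3.2 is silent on permanence.
- The list of changes in Appendix E alters neither sentence, so both are current.

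**4. Does relatedness separate the rules?** Section 6.1.7 defines a drug-related toxicity as one that the investigator or the sponsor judges to have a reasonable possibility of relationship. Section 6.1.7.4 opens by speaking of treatment-related events. Section 5.4.1 has no such condition. A severe reaction of clearly different cause can therefore be read as falling under Section 5.4.1 alone. A drug-related one falls under both, and there the conflict remains.

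**5. How large is it?** The conflict is one pair of sentences. No event rate can be derived. Section 3.2 states that "no systemic hypersensitivity or injection site reactions have been reported to date", and Section 6.1.7.3 states "No infusion reactions have occurred in the single dose PSP clinical study" and extends this to the expanded-access experience. The only bound available is on later exposure. Appendix C numbers the doses to 66. The count agrees with the schedule: 3 infusions by Day 29, plus (1793 − 29) / 28 = 63 more to Day 1793, gives 66. For a subject coming from placebo, a reaction at Dose 1 would leave at most 66 − 1 = 65 scheduled ABBV-8E12 infusions.

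**The case against.** The strongest reply is that the protocol does tell a site where to look. Sections 5.6.1 and 6.1.7 direct drug-related toxicity to a section that deals with allergic reactions by name, and a site that follows the direction reaches the mandatory stop. This stands in part. A reader might infer that the documents give no guidance on which rule to use, and that would be too strong. The direction is still not a precedence clause. Section 6.1.7 calls its content guidelines, and Section 5.4.1 is the section headed for discontinuation of individual subjects.

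A second reply is that the sections differ in scope: drug-related reactions under one, reactions of other cause under the other. This also stands in part. It narrows the conflict but does not remove it. It also bars another tempting inference, that Section 6.1.7.4 demands a permanent stop after any severe allergic reaction whatever its cause. Read with the introduction to Section 6.1.7 and its own opening sentence, Section 6.1.7.4 is about treatment-related events. A rule without that limit would remove a subject for a severe allergy clearly due to food, a sting or another medicine, in a disease with no approved treatment.

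A third reply is that the practical effect is small, and this is fair. A site that stops permanently satisfies both texts. The investigator may stop treatment at any time in the subject's interest. Harm would require a severe reaction, a decision taken under Section 5.4.1 alone, and a TA MD who allowed dosing to resume.

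**Conclusion.** The inconsistency is real and is worth correcting at the next amendment. For a severe or life-threatening allergic reaction related to study drug, Section 5.4.1 leaves to the TA MD a decision that Section 6.1.7.4 has already made. The pointers to Section 6.1.7 favour the mandatory rule without displacing the discretionary sentence.

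A reader might infer that Section 5.4.1 permits re-dosing after a severe reaction. It does not say so; it fails to rule it out. Nor do the documents support any forecast of harm.

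The consequence is confined to the event itself, should it occur. No estimate, sample size or analysis is affected. Confidence is high that the wording conflicts, and that confidence does not extend to any rate of harm. The conclusion assumes that no precedence statement stands in Protocol Sections 6.1.5 or 7.0, whose text was not available here.

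**What to change.** Replace the sentence in Section 5.4.1 with:

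> Severe or life-threatening allergic reactions for which the investigator or AbbVie judges a reasonable possibility of relationship to study drug require immediate interruption and permanent discontinuation of ABBV-8E12 per Section 6.1.7.4, and the AbbVie TA MD will be notified. Other adverse events that require immediate interruption will be considered by the AbbVie TA MD for permanent discontinuation, except where Section 6.1.7.5 already requires discontinuation. Appropriate medical therapy and follow-up will be initiated in all cases.

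This adopts the stricter rule that the sponsor has already written and keeps the relatedness test of Section 6.1.7. Reactions of disputed cause are still caught, because a judgment by either party is enough, and under Section 6.1.3 the sponsor treats an event with missing or unassessable causality as associated. The exception for Section 6.1.7.5 keeps the new text from making discretionary the stop already required for severe drug-related nervous system events.

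The cost is one passage of protocol wording at the next amendment. Visits, data collection, sample size and analysis do not change.
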